2.3.9.2. Death

Tabulations will be produced for all-cause mortality 30 and 60 days after the first dose, and within 30 days after the last dose, as well as all deaths for all subjects treated. The cause of death will also be summarized in this table. In particular, frequencies of deaths that are due to study treatment-related adverse events will also be reported.

2.3.9.3. Clinical Laboratory Tests

Laboratory data of hematology and clinical chemistry up to 30 days after last dose will be reported in SI units.

Summary statistics (N, mean, SD, median, and range) will be calculated for the raw data and for their changes from baseline by scheduled visits, as well as for last value and for the changes from baseline to the last value. Within a cycle, summary statistics from the worst values will be provided. Individual values outside the normal ranges will be identified (by “H” for high and “L” for low) in the data listings displaying the absolute values for each subject.

Displays of over-time summaries will be presented for the following key laboratory parameters: hemoglobin, white blood cell count, absolute neutrophil count, platelet count, manual percent immature myeloid cells (blasts, promyelocytes,

myelocytes,metamyelocytes and nucleated RBC), sodium, alkaline phosphatase, potassium, lactic acid dehydrogenase, blood urea nitrogen, albumin, creatinine, serum ferritin, alanine aminotransferase (ALT), aspartate aminotransferase (AST), total bilirubin (with fractionation if abnormal), INR(or PT) and aPTT • INR (or PT) and aPTT.

Shift tables for each cycle will be produced for selected laboratory parameters, to include hemoglobin, white blood cell count, neutrophils, platelet count, creatinine, total bilirubin, ALT, AST, lactic dehydrogenase, sodium, and potassium. These tables will summarize by cycle the number of subjects with each baseline CTC grade and changes to the maximum CTCAE grade in the cycle. For laboratory parameters without CTCAE grade, shifts from baseline to highest per cycle (Low, Normal, High) categories will be used.

Shift tables from baseline to worst value on treatment (from treatment start to 30 days after last dose or the end of treatment visit date, whichever is later) will also be provided. The worst toxicity grade during the treatment will be tabulated.

In addition, incidence of persistent (≥ 2 or 4 weeks) and severe (≥ 3 or 4 grade) cytopenia (thrombocytopenia/neutropenia) will be evaluated. Maximum post-baseline CTCAE grade for anemia, leukopenia, neutropenia, and thrombocytopenia will be tabulated.

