- Peripheral blood smear will be performed every 12 weeks up to Week 48, then every 24 weeks until disease progression or unacceptable toxicity and at time of CR/PR. Peripheral blood smear review will be performed by a central pathologist.
- MF Symptom Recall Form will be completed starting after Week 48, on Day 1 of every cycle at time of other PROs, and at time of CR/PR if occurring after Week 48.
- m EORTC QLQ-C30 questionnaire, EQ5D-5L, and BPI questionnaires on Cycle 1 Day 1 should be completed prior to the first dose of study treatment.
- ⁿ Week 24 PRO questionnaires should be performed the same day as Week 24 MRI.
- Hematology and chemistry laboratory assessments to determine subject eligibility must be performed within 21 days prior to randomization. The last result obtained prior to randomization will be used to determine eligibility. Hematology assessment for eligibility must be completed. For Cycle 1, Day 1 only, clinical laboratory hematology and chemistry assessments do not need to be repeated if the Screening tests were performed within 5 days of the first dose of study treatment. After Cycle 1, Day 1, required laboratory tests must be performed within 48 hours prior to the scheduled visit. For subjects with AST, ALT, ALP or bilirubin Grade ≥3, laboratory assessments need be to repeated weekly until bilirubin with fractionation is <3 x ULN, and AST, ALT and ALP are <5 x ULN. Subjects with Grade 1 and Grade 2 treatment emergent elevations in AST, ALT, ALP or bilirubin at time of treatment discontinuation should continue to have laboratory assessments monthly until resolution to at least baseline. For further guidance on liver function tests, see section on laboratory evaluations in Section 9.8. Subjects who have their dose increased from 4.7 mg/kg to 9.4 mg/kg must meet the eligibility criteria for hematologic laboratory values (inclusion criterion 8.1) and biochemical laboratory values (inclusion criterion 9.1) before starting treatment with 9.4 mg/kg.

25

- P An expanded liver panel should be performed at screening. Thereafter, if an adverse event of interest is reported, then an expanded liver panel should be performed which should include GGT, chloride, bicarbonate, magnesium, and fractionated bilirubin. The expanded liver panel will need to be repeatedly weekly until adverse event of interest has resolved.
- ^q Repeat INR (or PT) and aPTT during study if subject has a hemorrhagic event.

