All laboratory tests should be performed at the laboratory facilities associated with the investigational site. Laboratory certificates or accreditation and normal ranges of the laboratory facility at the site must be submitted to the sponsor before the enrollment of any subject at the site. If the subject has the laboratory assessments conducted at a laboratory facility other than the one associated with the investigational site, then the investigator must submit to the sponsor laboratory certificates or accreditation and normal ranges for that facility as well. The laboratory reports must be filed with the source documents.

Blood samples for serum chemistry and hematology to assess the safety of study treatment will be collected. Required laboratory tests must be performed within 48 hours prior to the scheduled visit. For Cycle 1, Day 1 only, clinical laboratory tests do not need to be repeated if the Screening tests were performed within 5 days of the first dose of study treatment.

The investigator must review the laboratory report, document this review, and record any clinically relevant changes occurring during the study in the adverse event section of the CRF. For example,

laboratory abnormalities leading to an action regarding any study treatment (dose reduction, temporary stop, delay of the start of a cycle or permanent stop) or the start of concomitant therapy should be reported. For each laboratory abnormality reported as an adverse event, the following laboratory values should be reported in the laboratory section of the CRF: the value indicative of the onset of each toxicity grade; the most abnormal value observed during the adverse event, and the value supporting recovery to Grade ≤ 1 or to baseline values.

The following tests will be performed by the local laboratory at the time points shown the Time and Events Schedule:

• Hematology Panel

-hemoglobin

-absolute neutrophil count (ANC)

-manual percent immature myeloid cells (blasts, promyelocytes, myelocytes, metamyelocytes and nucleated RBC) -white blood cell (WBC) count

-platelet count

• Serum Chemistry Panel

-sodium

-potassium

-blood urea nitrogen (BUN)

-creatinine

-alanine aminotransferase (ALT)

- total bilirubin (with fractionation at screening; with fractionation post-screening if

total bilirubin is abnormal)

-alkaline phosphatase (ALP)

-lactic acid dehydrogenase (LDH)

-albumin

-serum ferritin

-aspartate aminotransferase (AST)

• INR (or PT) and aPTT

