• Expanded LFT Panel

- gamma-glutamyl transpeptidase (GGT)

- magnesium

- chloride

- fractionated bilirubin

- bicarbonate

An expanded LFT panel is required for all subjects at screening and if an adverse event of interest is reported. For subjects with AST, ALT, ALP or bilirubin Grade ≥3, LFT laboratory assessments need to be repeated weekly until bilirubin with fractionation is <3x ULN, and AST, ALT and ALP are <5 x ULN. Additionally, subjects with Grade 1 and Grade 2 treatment emergent elevations in AST, ALT, ALP or bilirubin at the time of treatment discontinuation should continue to have laboratory assessments monthly until resolution to at least baseline.

• Viral hepatitis: Screening for hepatitis should include hepatitis serology panel A through E. Hepatitis D serology is only required if the subject tests positive for the hepatitis B surface antigen (HBsAg).

• Peripheral Blood Smear: A peripheral blood smear should be performed at the time points shown in the Time and Events Schedule.

Electrocardiogram (ECG)

A 12-lead ECG will be performed at Screening. During the collection of ECGs, subjects should be in a quiet setting without distractions (eg, television, cell phones). Subjects should rest in a supine position for at least 5 minutes before ECG collection and should refrain from talking or moving arms or legs. If blood sampling or vital sign measurement is scheduled for the same time point as ECG recording, then the procedures should be performed in the following order: ECG(s), vital signs, blood draw.

Vital Signs

Temperature, pulse/heart rate, and blood pressure will be recorded, preferably while the subject is seated, at the time points specified in the Time and Events Schedule. Vital signs that are considered to be clinically relevant by the investigator are to be documented as adverse events.

Physical Examination

Screening physical examination should include body weight, height, and the evaluation of head, eye, ear, nose, and throat (HEENT), cardiovascular, dermatological, musculoskeletal, respiratory, gastrointestinal, and neurological systems. Only a limited symptom-directed physical examination including spleen palpation and weight assessment is required on Day 1 of all cycles after baseline. New or worsened abnormalities should be recorded as adverse events if appropriate.

ECOG Performance Status

The ECOG performance status scale will be used to grade changes in the subject's activities of daily living.

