2.1. General Analysis Definitions

2.1.1. Baseline, Treatment Phase and Posttreatment Follow Up Phase

Unless specified otherwise, the baseline value is defined as the last non-missing value collected on or before the administration of the first dose of study drug. For subjects who have been randomized but not treated with any study drug, the randomization date will be used as the reference date for baseline value calculation.

The treatment phase begins on date of Cycle 1, Day 1 and continues until study drug discontinuation.

The Posttreatment follow up phase starts from the day after study drug discontinuation until death, lost to follow-up, withdrawal of consent or study end, whichever occurs first.

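### Bilirubin fractions are measured in everyone at screening but selectively afterwards, so summarizing them over time as SAP 2.3.9.3 indicates is expected to show a rise without any drug effect

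*SAP*

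**What the plan says.** **Collection.** The serum chemistry panel in Protocol 9.8 specifies "total bilirubin (with fractionation at screening; with fractionation post-screening if" total bilirubin is abnormal. The expanded liver panel also contains fractionated bilirubin and has the same shape: "An expanded LFT panel is required for all subjects at screening and if an adverse event of interest" is reported. Footnote p of the main-study Time and Events Schedule agrees ("An expanded liver panel should be performed at screening", then event-triggered and repeated weekly until the event resolves). The adverse events of interest are Grade 3 or higher ALT, AST, ALP or bilirubin, and all hepatic adverse events.

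**Analysis.** SAP 2.3.9.3 says summary statistics "will be calculated for the raw data and for their changes from baseline by scheduled visits", and also for the last value and its change from baseline. It adds: "Displays of over-time summaries will be presented for the following key laboratory parameters". That list includes "total bilirubin (with fractionation if abnormal"). Under SAP 2.1.1, "the baseline value is defined as the last non-missing value collected on or before the administration of the first dose of study drug", so the screening sample gives essentially every subject a baseline fraction. SAP 2.1.3 imputes only certain dates, so a visit without a fraction drops out. Nothing restricts the fractions to a comparable set of subjects, confines them to listings, or addresses the changing denominator.

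**The concern.** Baseline describes the whole treated group. Each later visit describes mainly those whose total bilirubin was abnormal at that visit. Total and direct bilirubin are correlated, so the later sample is selected on something close to the outcome. The raw mean then steps up at the first post-baseline visit in both arms. The paired change is biased the same way, because a subject contributes a visit only when the value happens to be high. The last-value summary has a related problem: if it takes the last non-missing result, a subject whose bilirubin normalizes keeps the last fraction taken while total bilirubin was abnormal.

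Hepatic safety is a stated concern (Protocol 1.1.5.3.3), and an Independent Hepatic Expert Committee has been set up. Both arms receive imetelstat, so no untreated group would show the artefact for what it is.

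**Working it through.** The plan gives no figure to reproduce, and no bilirubin distribution. All sizes below are therefore assumption-based and assume **no drug effect**.

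**Model A, closed form.** Log total and log direct bilirubin are normal and stationary. Let *p* be the share of subjects with total above ULN at a visit, *c* = z(1−*p*), and *a* = (total–direct correlation) × (SD of log direct). Let ρ be the within-subject correlation between visits.

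- Raw ratio (measured post-baseline mean ÷ all-subject baseline mean) = Φ(*a* − *c*) / *p*
- Paired change as a share of the baseline mean = [Φ(*a* − *c*) − Φ(ρ*a* − *c*)] / *p*

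Assumed SD 0.6 and correlation 0.8 give *a* = 0.48. Correlation 0.5 gives *a* = 0.30.

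| *p* | *c* | Φ(0.48 − *c*) | raw ratio, *a* = 0.48 | raw ratio, *a* = 0.30 (simulated) |
|---|---|---|---|---|
| 0.2 | 0.842 | 0.359 | 1.79 | 1.46 |
| 0.4 | 0.253 | 0.590 | 1.47 | 1.30 |
| 0.6 | −0.253 | 0.768 | 1.28 | 1.18 |
| 0.8 | −0.842 | 0.907 | 1.13 | 1.09 |

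Simulation gave the same ratios for *a* = 0.48. For the paired change at *p* = 0.2 and ρ = 0.7: (0.359 − 0.307)/0.2 = 0.26. Across *p* = 0.2–0.8 and ρ = 0.5–0.9 it runs from +1% to +43%.

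**Entry limits.** Protocol inclusion criterion 9.1 caps total bilirubin at 3 × ULN and direct at 2 × ULN. Applying the caps moves the paired range to +6% to +47%. Part of that is regression to the mean: with fractions measured in everyone at every visit, the capped ratio is already 1.00–1.16, against 1.00 without caps.

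**Event-triggered panels.** Adding fractions in a further 10% of subjects irrespective of total bilirubin lowers the raw ratio to 1.51, 1.37 and 1.24 at *p* = 0.2, 0.4 and 0.6.

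**Model B.** Between-subject log-SD is 0.45, within-subject log-SD 0.15–0.30, direct is 35% of total, and entry is capped at 3 × ULN total. The raw ratio is about 1.9–2.0 at 14–17% abnormal, about 1.6 at 32–34%, and about 1.4 at about 49%. The paired change, relative to the measured subjects' own baseline, is +3% to +22%, against a true 0–2%. With 12 assumed visits, the change to the last measured value is +7% to +37%.

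**Trial-sized samples.** Model A without caps was run with arms of 48 and 59 (an assumed split of the 107 enrolled) and *p* = 0.2–0.6. The raw mean rose in 99–100% of null trials and the paired mean change in 65–94%.

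**A simplification.** Both models use one baseline draw from everyone. Chemistry is also taken on Cycle 1 Day 1 unless screening was within 5 days. If a fraction taken then because total was abnormal replaces the screening one, baseline is itself slightly selected. Rerunning Model B that way lowers both contrasts, the paired one by roughly half, and removes neither.

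**The case against.** The strongest reply is that the SAP may not plan this display at all. It names total bilirubin, never direct bilirubin. The parenthesis may only echo the protocol's panel label, and the shift-table list in the same section says simply total bilirubin. Read narrowly, the words could limit the fractions to abnormal totals at baseline as well. The raw ratio is then 1.00, or 1.01–1.18 with the entry caps. That reading is possible. But the general sentence on raw values and changes covers clinical chemistry as a whole, and nothing in the SAP adopts the narrow reading.

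A reader might infer more than the documents support:

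- *That every later fraction comes from a subject with abnormal total bilirubin.* The expanded panel can be triggered by other liver events. Those subjects are also selected, but not on total bilirubin, and they dilute the effect.
- *That a real hepatic effect could not be recognized.* Total bilirubin is on the chemistry panel for everyone. It is summarized over time and in shift tables, Grade 3 or higher elevations are adverse events of interest, hepatic events are tabulated, and the Hepatic Expert Committee reviews liver data at least quarterly. The reported N would also expose the falling denominator, though it would not correct for it.
- *That the mean doubles.* A ratio near 2 needs only 14–17% of visits to be abnormal. The Amendment 1 rationale describes bilirubin abnormalities as highly prevalent in this population. Total bilirubin worsened in 48.5% of the prior study's subjects, although that counts any worsening, not abnormality per visit. Both point towards smaller ratios.
- *That the paired change must rise.* This is an expectation, not a certainty, in arms of this size.

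**Conclusion.** The point holds for one descriptive element: the bilirubin fractions in the over-time, change-from-baseline and last-value summaries, if these are produced as the text indicates. The upward direction follows from selective measurement and a positive total–direct correlation. It fades only as nearly everyone comes to have abnormal total bilirubin. The size, a raw ratio of about 1.1 to 2.0 and a smaller upward bias in paired change, rests wholly on assumed distributions. Total bilirubin summaries, shift tables and CTCAE grading, hepatic adverse event tabulations and the co-primary analyses are unaffected. It is worth correcting because it concerns liver safety in a trial without an untreated arm, and because the wording is ambiguous enough to be programmed this way.

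**What to change.** In SAP 2.3.9.3, keep total bilirubin, all subjects, as the over-time parameter. State that the fractions are excluded from the mean, change-from-baseline and last-value summaries and shown in the individual listings, which are already planned with high and low flags.

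Optionally, add the number of Treated subjects with any measured post-baseline direct bilirubin above stated multiples of ULN, with the number measured alongside. Visits without a fraction should not be counted as normal unless a footnote states that as an assumption: direct bilirubin has its own limit and could exceed it while total is normal.

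An alternative is to summarize fractions only among subjects with abnormal total bilirubin at both baseline and the visit, showing n. In Model A this brings the null paired change to about zero without the entry caps, but leaves +2% to +23% of the baseline mean with them. It also omits subjects whose bilirubin first becomes abnormal on treatment.

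The cost is a few lines of SAP text and at most one table, with no new data. The loss is an all-subject mean-over-time display of direct bilirubin, which the collection schedule cannot support in any case.

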The analysis for the co-primary endpoints (spleen response rate and symptom response rate) will be based on the Treated Population. For each treatment arm, spleen response rate and symptom response rate will be presented along with their 95% 2-sided exact confidence interval. The spleen response data reviewed by the Independent Review Committee (IRC) will be used for the primary analysis, the interim data reviews, and the final analysis. The symptom response data measured by the modified MFSAF v2.0 Total Symptom Score (TSS) will be calculated as the 7-day average of daily TSS, which is the summation of 6 individual symptom scores. Additional analyses will be performed for subjects initially treated with imetelstat 4.7 mg/kg who had their dose increased to 9.4 mg/kg as described in Section 6 (Dosage and Administration) of the protocol.

EudraCT NUMBER: 2015-000946-41

TIME AND EVENTS SCHEDULE (MAIN STUDY)

Beginning with Amendment 3, follow the Time and Events Schedule for the Extension Phase.

PHASE	Screening Phase	Treatment Phase ^a (21-day treatment cycle)						Posttreatment Follow-up Phase ^b
		Cycle 1	Cycle 1	Cycle 2	Cycle 3 until End-of-Treatment	Dose Escalation ^w (4.7 to 9.4 mg/kg)	End-of-Treatment Visit	
	Day -21 to -1	Day 1	Day 8, 15	Day 1, 8, 15	Day 1		Within 30 days after last dose	Every 16 weeks
Study Procedures		3	,	3 / /				,
Screening/Administrative								
Informed consent	X							
Inclusion/exclusion criteria	X							
Medical history and demographics	X							
ECOG performance status	X	X		X (D1 only)	X		X	
Transfusion history and status ^c	X	X	X	X	X			
Hepatitis serologies ^d	X							
Pregnancy test	X							
Screening Myelofibrosis								
Symptom Form ^e	X							
Study Drug Administration								
Randomization		Xa						
Dispense/administer study drug		X		X (D1 only)	X			
Safety Assessments								
Physical examination including spleen palpation ^f	X	X		X (D1 only)	X		X	
Vital signs ^g	X	X		X (D1 only)				
12-lead ECG	X							
Efficacy Assessments								
Abdominal MRI ^h	X	Every 12 we	Every 12 weeks up to Week 48 then every 24 weeks and at time of CR/PR X				3 months posttreatment	
Spleen palpation ⁱ	X	Every 12 we	Every 12 weeks up to Week 48 then every 24 weeks and at time of CR/PR				3 months posttreatment	
BM aspirate and biopsy ^j	X	Every 24 weeks and at time of CR/PR X (if feasible)						
Peripheral blood smear ^k	X	Every 12 we	eks up to Week	48 then every 24 CR/PR		X		

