9.1.3. Single-Blind Treatment Phase

Day 1/Day of Randomization/Registration

This was originally a single-blind study, in which subjects were blinded to the treatment arms. Beginning with Protocol Amendment 2, neither subjects nor investigators will be blinded to subject treatment assignment. The Treatment Phase will begin at randomization/registration and will continue until study drug discontinuation. Subjects should start study treatment within 72 hours after randomization/registration in the IWRS.

Treatment Phase

A cycle is defined as 21 days. Details of the procedures performed during the Treatment Phase are outlined in the Time and Events Schedule. A window of ± 3 days is allowed for visits to the clinic. Subjects will be closely monitored for adverse events, laboratory abnormalities, and clinical

response. It is recommended that the EORTC QLQ-C30, EQ-5D-5L, BPI, PGIC, and MF Symptom Recall Form are administered before any tests, procedures, or other consultations. After the PRO questionnaires have been administered, a symptom-directed physical examination including spleen palpation will be conducted (see Section 9.2.1). Laboratory test results must be reviewed prior to administering study treatment. Adverse events and changes to concomitant medications will be recorded (see Section 17.5). Dose modifications will be made according to criteria described in Sections 6.1, 6.2, and 6.3. The investigator will assess subject response to therapy using the efficacy measurements and disease response criteria according to the schedule described in Section 9.2.1.

Clinical evaluations and laboratory studies may be repeated more frequently, if clinically indicated. If a subject develops features of response (eg, improvement in palpable or radiographic splenomegaly, improvement of symptoms, resolution of leukoerythroblastosis, decreased transfusion requirements, etc.) and CR or PR are clinically suspected at a time not specified on the Time and Events Schedule then all required disease assessments should be performed. In order to confirm a CR or PR per modified IWG-MRT criteria, all disease assessments should be repeated 12 weeks from time of CR or PR. If progressive disease is diagnosed, or the subject discontinues study treatment for other reasons, then the subject will complete the End-of-Treatment Visit within 30 days after the last dose of study treatment, and enter the Posttreatment Follow-up Phase.

End-of-Treatment/Early Withdrawal

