2.1.5. Other General Definitions

2.1.5.1. Individual Study Start/Treatment Start (Day 1), Study Day and Month

Individual Study Start /Treatment start is the date of the Cycle 1, Day 1. If study drug was not administered to a subject, study start is defined as the date of randomization.

The study day is equal to the date of the procedure minus the date of study start plus 1.

A month is defined as 365.25/12 days.

2.1.5.2. End of Treatment, End of Study, Time on Treatment , and Time on Study for Individual Subject

For each individual subject, disposition definitions are defined as below:

End of treatment is defined as the date of the last dose of the study drug. The end of Study is the date of death or the date last known to be alive, defined as the maximum date of the following study evaluations: randomization, vital signs, ECOG performance status, MRIs, physical examination, bone marrow evaluations, labs (hematology, chemistry), study drug administration, subsequent therapy, investigator-assessed PD, relapse from CR, investigator determined response, and survival follow-up.

The treatment cycle is defined as 21 days.

Time on treatment (in weeks) is equal to (the end date of treatment – the date of Cycle 1, Day 1 + 1)/7.

Time on study (in months) is equal to (the end date of follow-up – the date of Cycle 1, Day 1 + 1)/30.4375.

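### By-cycle worst-grade laboratory tables will step down at Cycle 3 even with unchanged toxicity, because scheduled draws fall from three per cycle to one

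*SAP*

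**What the plan says.** SAP 2.3.9.3 (Clinical Laboratory Tests) contains two by-cycle displays built on extremes. First, "Shift tables for each cycle will be produced for selected laboratory parameters", including hemoglobin, white cells, neutrophils, platelets, creatinine, bilirubin, ALT and AST. For each cycle they count subjects at each baseline grade and show "changes to the maximum CTCAE grade in the cycle". Second, "Within a cycle, summary statistics from the worst values will be provided".

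The sampling comes from the Protocol's Time and Events Schedule (Main Study). Hematology and chemistry are marked for Day 1 and Days 8 and 15 of Cycle 1. In Cycle 2 they carry an unrestricted mark under a Day 1, 8, 15 column, where neighbouring rows such as INR are limited to Day 1. The next column, "Cycle 3 until End-of-Treatment", has Day 1 only. Footnote o to that schedule says "After Cycle 1, Day 1, required laboratory tests must be performed within 48 hours prior to the scheduled visit", and Protocol 9.1.3 adds "Laboratory test results must be reviewed prior to administering study treatment". The later Day 1 value is therefore a pre-dose value. SAP 2.1.5.2 sets the interval: "The treatment cycle is defined as 21 days".

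The SAP does not limit the by-cycle maximum to a common day, does not allow for the number of draws, and does not say to which cycle a pre-dose or unscheduled value belongs. Its only visit-window table (SAP 2.1.2) lists vital signs.

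**The concern.** A maximum depends on how many values it is taken over. With three scheduled values in Cycle 2 and one in Cycle 3, the by-cycle rate of severe abnormality should drop between those columns even if every dose does the same harm. The single later value is also taken about three weeks after the previous dose, so no mid-cycle count is scheduled from Cycle 3 on.

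Protocol 1.1.5.3.1 describes cytopenias, thrombocytopenia above all, as dose-limiting. SAP 1.2 says that the development decision will draw on all the data, with safety and blood counts among them. A reader who sees Grade 3–4 cytopenia fall from Cycle 2 to Cycle 3 could conclude that toxicity wanes with continued dosing, when the fall may come from the schedule alone.

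**Working it through.** **1. Check the schedule against the plan's own count.** Protocol Table 8 gives 19 hematology samples per subject, based on a median of 12 cycles and including the end-of-study visit. Counting the schedule: screening 1 + Cycle 1 (3) + Cycle 2 (3) + Cycles 3–12 (10 × 1) + End-of-Treatment 1 = 18. One dose-escalation draw, or a thirteenth cycle, gives 19. Three draws in all 12 cycles would need 1 + 36 + 1 = 38. Table 8 therefore supports the reading of 3, 3, 1, 1, … draws per cycle.

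**2. Count the post-baseline draws.** SAP 2.1.1 takes as baseline the last value on or before the first dose. Cycle 1 Day 1 is normally that value, and footnote o waives it if screening tests were done within 5 days of the first dose. Cycle 1 thus has two post-baseline draws (Days 8 and 15), Cycle 2 has three, and each later cycle has one.

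**3. Compute the by-cycle rate at constant toxicity.** Let p be the chance that any one draw shows Grade 3 or higher, the same on every day and in every cycle. The documents give no such figure, so p is assumed and a range is shown.

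- Independent draws: P(at least one in n) = 1 − (1 − p)^n. At p = 0.10: n = 3 gives 1 − 0.9³ = 27.1%; n = 2 gives 1 − 0.9² = 19.0%; n = 1 gives 10%.
- Correlated draws: 1 − Φₙ(t, …, t; ρ), with t = Φ⁻¹(1 − p) and a common within-cycle correlation ρ on a normal scale.

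| p | Cycle | ρ = 0 | ρ = 0.5 | ρ = 0.8 | ρ = 0.95 |
|---|---|---|---|---|---|
| 5% | 1 (two draws) | 9.8% | 8.8% | 7.5% | 6.3% |
| 5% | 2 (three draws) | 14.3% | 11.8% | 9.3% | 7.1% |
| 5% | 3 onward (one draw) | 5% | 5% | 5% | 5% |
| 10% | 1 | 19.0% | 16.8% | 14.4% | 12.2% |
| 10% | 2 | 27.1% | 21.8% | 17.2% | 13.5% |
| 10% | 3 onward | 10% | 10% | 10% | 10% |
| 20% | 1 | 36.0% | 31.3% | 27.1% | 23.5% |
| 20% | 2 | 48.8% | 38.9% | 31.3% | 25.5% |
| 20% | 3 onward | 20% | 20% | 20% | 20% |

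At p = 10%, the true per-draw rate at Cycle 3 would have to rise to between 13.5% and 27.1% to hide the step from Cycle 2 across these correlations.

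**4. Check the direction without the model.** The Cycle 2 draws include a Day 1 pre-dose value of the same kind as the Cycle 3 draw. The maximum of the three cannot be below that value. With constant toxicity the step from Cycle 2 to Cycle 3 is therefore downward, or zero only if every Grade 3 or higher result on Day 8 or 15 is matched by one on Day 1. The step from Cycle 1 does rest on the equal-p assumption.

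**5. Check the assignment of the pre-dose value.** If each pre-dose value is assigned to the preceding cycle, Cycles 1 and 2 hold roughly Days 8, 15 and 22, and later cycles hold Day 22 alone. The ratio is again 3 to 1.

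**The case against.** The best case against acting is that these tables are descriptive and SAP 2.3.9.3 already plans displays free of this step. It plans summaries of raw values and changes at each scheduled visit, over-time displays of the main parameters, shifts to the worst value on treatment, maximum post-baseline cytopenia grade, and persistent and severe cytopenia. The listed adverse event tabulations in SAP 2.3.9.1 are not by cycle, and no test or stated decision rule uses the by-cycle shifts. All of that stands, and it limits the consequence. What is missing is a by-cycle grade table that compares like with like.

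A second objection is that independence is the largest case shown. Counts from one subject a week apart are correlated, and at correlation 0.95 the step at p = 10% is only 13.5% against 10%. That stands on size, not direction.

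Third, extra tests are allowed when clinically indicated (Protocol 9.1.3), and a Grade 3 or higher AST, ALT, ALP or bilirubin triggers weekly repeats (footnote o). Such tests may narrow the step, but they follow events and do not restore equal sampling. Protocol Sections 6.1 to 6.3 are not in the text supplied, so monitoring required there cannot be judged either way.

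Two stronger readings are tempting. A reader might infer a sharp artificial drop in severe liver abnormalities. The documents show no mid-cycle liver peak. In the earlier myelofibrosis study no subject had Grade 3 or higher AST or ALT and three had Grade 3 events, two in ALP and one in bilirubin (Protocol 1.1.5.3.3). ALP is also not among the parameters named for the by-cycle shifts. A reader might also infer that the SAP credits each pre-dose value to the cycle about to start. It states no rule, and a draw up to 48 hours before the visit could fall in the preceding cycle under a date-based derivation.

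**Conclusion.** The point holds for the by-cycle worst-grade and worst-value displays. The schedule builds in a tendency for apparent severe toxicity to fall at Cycle 3, and no SAP rule corrects it. The practical weight lies mainly with cytopenias.

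The direction from Cycle 2 to Cycle 3 follows from the schedule when toxicity is constant; a large enough true rise could mask it. The size rests on an assumed per-draw rate and correlation. The documents give no within-cycle course of counts, so the figures illustrate the step and do not predict it.

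A reader might go further and infer that the overall safety conclusions are biased. The documents do not support that. The by-visit summaries and the worst-on-treatment tables have no such step, although later mid-cycle low points are less likely to be captured anywhere. No efficacy result is touched.

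**What to change.** In SAP 2.3.9.3:

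- Add a grade shift table for trends across cycles that uses only the scheduled Day 1 pre-dose value from Cycle 2 onward, attributed to the preceding dose.
- Present the worst Day 8/15 grades in a separate table limited to Cycles 1 and 2.
- State how pre-dose and unscheduled values are assigned to cycles, and whether unscheduled values enter the by-cycle maximum.
- Footnote the change in sampling at Cycle 3 on every by-cycle worst-grade or worst-value display.
- Keep the worst-on-treatment shift table as planned.

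With one comparable draw per cycle, the expected rate at constant toxicity is p in every column and the step disappears. The cost is SAP wording and one extra table, with no new data. The drawback is that the Day 1 table does not show mid-cycle low points, which is why the Day 8/15 results need their own display.
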